## 7.0 Adverse Events

For purposes of this clinical trial record only AE's possibly, probably, or definitely related to the visit 1 and visit 2 PET/CT scans. Possibly, probably or definitely related AE's must be followed until resolution or 30 days after visit 2 whichever comes first.

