### 2.2 Secondary Objectives

- To evaluate the ability of PET-CT to reproducibly determine dose to tumor, normal liver, and other surrounding organs
- To determine the stability of microsphere location by examining the changes in dose in a subset of patients with PET-CT scans performed on Day 0 and Day 1
- To determine the relationship of dose predicted by Tc-99m labeled Macro-aggregated albumin (MAA) imaged using SPECT versus post-treatment dosimetry
- To determine the effect of dose delivered on local control and normal tissue complications
- To measure the perfusion of the tumor for correlation with dose deposition, based on arterial phase CT measurements
- To evaluate overall survival for 5 years after Visit 1, Day 0.

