### **Visit 2 (Day 1)**

Visit 2 will take place on Day 1, and will be pursued in only a subset of patients. This will include only a PET-CT for the purposes of determining the stability of microsphere

placement. The Visit 2, Day 1 PET-CT should be scheduled 24 hours +/- 3 hours after the Visit 1, Day 0 post-treatment PET-CT.

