## 6.0 Study Calendar

	Registration Visit	Pre treatment Visit(s)	Visit 1 / Day 0	Visit 2/ Day 1	Follow up
Informed consent & HIPAA A	X				
Medical history	X				
Symptom Guided Physical exam G	X				X
ECOG Performance Status	X				X
CBC w/diff, plts B	X				X
Serum chemistry B	X				X
EKG (as indicated)	X				
β-HCG	X E				
Coagulation Studies B	X	X			
3 Phase Liver CT Simulation		X			
Staging Angiogram		X			
Coil Embolization		X			
Tc-99m (approx 5mCi) MAA Injection		X			
Planar and SPECT Imaging of Liver		X			
Adverse Event Assessment			X	X	X H
PET-CT C,D			X	X	
Tumor Imaging F	X				X I

A: Must be completed less than 28 days prior to registration and prior to any protocol specific tests or procedures.  B: CBC and CMP will be drawn at each follow-up visit, Coagulation studies include PT and INR. Coagulation studies must be performed for eligibility however results will not exclude patient participation.  C: Visit 1, Day 0 post treatment PET CT and contrast CT for subset of participants, Day 1 PET CT.  D: 24 hours +/- 3 hours after Day 0  E: See Section 4.4 for more information – Must be negative within 72 hours of first treatment related procedure or scan  F: Repeat imaging is encouraged to be the same modality (PET-CT, MRI, or contrast CT) as that in baseline study.  G: Physical exam with investigator where he/she reviews symptoms with the participant and addresses any issues that are identified by the participant. This is not the same as a complete physical exam, intentionally.  H: Record only AE's possibly, probably, or definitely related to the visit 2 / day 1 PET/CT scan. Possibly, probably or definitely related AE's must be followed until resolution or 30 days after visit 2.  I: Follow up tumor imaging begins with the month 3 follow up visit.
					

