## 8.0 Statistical Considerations

In this study, we will evaluate the dosages received by tumors and surrounding tissue using PET-CT data. The primary objective is to determine the relationship between radiation dose to 70% of the tumor volume and local control at 6 months. We will conduct this analysis at the tumor level, as different tumors may receive different doses of radiation, and may have different progression statuses at 6 months. We will use standard summary measures such as means, medians, ranges, and standard deviations to characterize the dosages received by tumor and other tissue. We will use percentages and frequency tables to evaluate other characteristics such as tumor histology, number of liver tumors per patient, and volume of liver tumors.

We will determine the relationship between radiation dose and local control at 6 months using regression models with Generalized Estimating Equations (GEE) to account for within-patient correlation. We will use logistic regression to adjust for potentially confounding factors such as tumor volume, primary histology, and SIR-Spheres versus Therasphere intervention. We will also determine the relationship between radiation dose to healthy tissue, and side effects such as fatigue, nausea, pain and elevated liver function tests. Each

side effect will be characterized as present or absent, and we will test the relationship between radiation dose to the relevant type of healthy tissue and each side effect. For example, we will look at the relationship between dose to the normal liver and elevation of liver function tests.

In further secondary analyses, we will explore the relationship between the distribution of activity measured by PET-CT, and the distribution predicted by T-99m labeled MAA. This can be translated into predicted dose. We will calculate differences between PET-CT and MAA doses, and present the data graphically. We will use the method proposed by Bland & Altman (2007) to assess the agreement between the two methods. Finally, in a subset of patients, we will explore the change in dose measured by PET-CT scan between day 0 and day 1. The dose at day 1 will be adjusted to account for the decay of the yttrium-90 using  $A=A_0e^{-(0.693t/T_{1/2})}$ . Observed changes in dose may be due to microsphere migration, and our main interest is to look for a systematic change in dose received based on this migration.

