#### Sample size considerations

We will power our study to detect a 10 Gy difference in mean radiation doses between tumors with local control and 6 months vs those which progressed. Based on preliminary data, we expect that the standard deviation of doses will be 12Gy, and that approximately 60% of tumors will retain local control at 6 months. We will use a two-sided test with type I error of 0.05. In preliminary data, within-patient correlation was 0.6-0.7, and we saw an average of 2 tumors per patient. We therefore will enroll 43 patients in this study to have approximately 80% power to detect a difference of 10 Gy.

It is anticipated that 10 patients will be recruited for Day 1 PET-CT studies. This number of patients would be expected to detect a difference in the range of 12-20 Gy (Day 0 – Decay-adjusted day 1). Although we may not get a significant result, the point estimates may give an indication of whether the microspheres are moving. This level of certainty is felt to be appropriate for an exploratory aim.

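### Section 8.0 tests healthy-tissue dose against fatigue, nausea and pain, but adverse event recording is limited to PET/CT-related events and no other structured source for these symptoms is specified

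*Combined protocol and SAP*

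**What the plan says.** One secondary objective in Section 2.2 reads: "To determine the effect of dose delivered on local control and normal tissue complications". Section 8.0 turns the toxicity half of it into an analysis of the "relationship between radiation dose to healthy tissue, and side effects such as fatigue, nausea, pain and elevated liver function tests". On coding, the same section says that every such "side effect will be characterized as present or absent"; the binary result is then tested against dose to the relevant healthy tissue.

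The recording rules are narrower:

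- **Section 7.0:** "For purposes of this clinical trial record only AE's possibly, probably, or definitely related to the visit 1 and visit 2 PET/CT scans".
- **Section 7.2.1, items 1 to 3:** the same restriction to the research scans applies to classifying events, to the adverse event case report form and to serious event forms.
- **Section 6.0, note H (follow-up visits):** "Record only AE's possibly, probably, or definitely related to the visit 2 / day 1 PET/CT scan". Under Section 5.0, "Visit 2 will take place on Day 1, and will be pursued in only a subset of patients"; the sample size text says "It is anticipated that 10 patients will be recruited for Day 1 PET-CT studies", out of 43 enrolled.

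The only other scheduled contact about symptoms is medical history at registration and the symptom-guided examination at registration and follow-up (Section 6.0, note G). No symptom list, grading, time window or form field is attached to either. Liver function is different: Sections 5.0 and 6.0 schedule a chemistry panel at registration and at every follow-up visit.

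**The concern.** The recording rule filters on the wrong cause for this analysis. Section 8.0 needs symptoms that radiation to normal tissue may have produced. Sections 6.0 and 7.0 tell sites to record only events that the scan may have produced. Nausea that an investigator attributes to the microspheres is the outcome of interest, and the rule excludes it.

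Limiting safety reporting to the scans is coherent in itself, because Section 3.0 makes the treatment standard care. The gap is that nothing else is specified to supply the outcome data. If blanks are then read as absent, the symptom outcome is misclassified. Where capture is unrelated to dose, the difference in symptom rates shrinks and power is lost. Where capture is related to dose, bias can go in either direction.

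**Working it through.** **1. Does each Section 8.0 outcome have a source?**

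| Outcome | Adverse event form | Other scheduled source |
|---|---|---|
| Fatigue, nausea, pain | Only if at least possibly related to a research PET/CT | Clinic notes from the symptom-guided examination; no structured recording or abstraction specified |
| Elevated liver function tests | Same limit | Chemistry panel at registration and each follow-up visit; no cut-off for elevated given |

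The gap is therefore confined to the three symptoms.

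**2. The plan's own figures.** No power is stated for the side-effect tests, so there is nothing to reproduce for them. The primary power statement reproduces: 43 × 2 = 86 tumours; at correlation 0.7 the design effect is 1 + (2 − 1) × 0.7 = 1.7; 86/1.7 = 50.6 effective tumours. With a 60:40 split, a 10 Gy difference and SD 12 Gy, noncentral-t power is 81.2%, against roughly 80% stated. It has no bearing on this point.

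**3. Illustration: capture unrelated to dose.** These inputs are assumptions: 21 low-dose and 22 high-dose patients (43 split at the middle), unrecorded symptoms coded absent, recorded rate = capture × true rate. Pooled chi-square test, two-sided 0.05, exact binomial enumeration:

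| True rates, low v high dose | 100% capture | 75% | 50% | 25% |
|---|---|---|---|---|
| 30% v 70% | 80.8% | 55.4% | 32.5% | 17.4% |
| 30% v 60% | 55.8% | 34.8% | 21.7% | 12.1% |
| 30% v 50% | 28.9% | 18.2% | 13.3% | 7.8% |

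For 30% v 70% the observed difference is 40, 30, 20 and 10 points (at 50% capture: 0.5 × 70 − 0.5 × 30 = 20). The odds ratio falls 5.4, 3.8, 3.1, 2.6, while the rate ratio stays at 70/30 = 2.33. Fisher's exact test gives lower power throughout: 70.9, 44.8, 25.4 and 9.5% for the first row.

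**4. Illustration: capture related to dose.**

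| True rates, low v high | Capture, low v high | Recorded rates | Chi-square rejects | Fisher rejects |
|---|---|---|---|---|
| 50% v 50% | 50% v 50% | 25% v 25% | 4.9% | 3.5% |
| 50% v 50% | 50% v 75% | 25% v 37.5% | 13.9% | 9.8% |
| 50% v 50% | 25% v 75% | 12.5% v 37.5% | 48.1% | 39.7% |
| 30% v 70% | 75% v 25% | 22.5% v 17.5% | 6.4% | 5.7% |

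The second and third rows are false positives. In the last row a true +40-point difference appears as −5 points.

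**5. Side issue: scope and window of adverse event recording.**

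| Place | Scans covered | Followed until |
|---|---|---|
| 6.0, note H | Visit 2 only | Resolution or 30 days after visit 2 |
| 7.0 | Visits 1 and 2 | "followed until resolution or 30 days after visit 2 whichever comes first" |
| 7.2.1, item 2 | Research PET/CT scans | Resolution, over the whole study |

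On the sample size text, 43 − 10 = 33 patients (33/43 = 77%) are not expected to have a day 1 scan. For them, note H leaves nothing recordable at follow-up and the 30-day limit has no starting point. This figure measures the inconsistency in scope. It does not measure the symptom gap, which affects all 43 patients. It is also approximate, because Section 5.0 allows further scans after a second treatment.

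**The case against.** The strongest reply is that the protocol text shows only that no structured source is named, not that the data will be missing. The case report forms and the study spreadsheet were not available. Section 9.1 says the spreadsheet holds all patient information, and part of Section 7.2 is missing from the text reviewed. Investigators review symptoms at registration and from one week onward, so abstracting clinic notes is a plausible route in a registry study. This stands as a limit on certainty. It does not close the gap: an examination guided by what the participant raises does not separate a symptom that was absent from one that was never asked about.

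It is also fair to say that the rates, the capture levels and the dose split are assumed. Section 8.0 does not say that dose will be dichotomised or that blanks will be coded absent. The 48.1% figure needs a threefold difference in capture for which the documents offer no mechanism, and Fisher's test lowers it to 39.7%. The figures show direction and plausible scale only.

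Lastly, this is a secondary analysis with no stated power, and full capture would still give only 28.9% power for 30% v 50%. That supports treating the point as short of critical. It does not justify leaving a planned test without a defined outcome source.

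**Conclusion.** The concern holds. Followed as written, the recording rule excludes the symptom data that a stated secondary analysis needs, and no replacement source is specified. It should be fixed, but it does not threaten the primary objective, and the laboratory data for the liver function analysis are already scheduled.

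The finding itself rests on the text alone. Its numerical size cannot be derived from the documents. Under the assumptions shown, halving capture takes power from 80.8% to 32.5% for 30% v 70%, and capture that varies with dose can create or reverse an association. The main condition is the unseen case report forms: if they already hold a structured symptom field, the defect reduces to wording.

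**What to change.** Keep the PET/CT limit for adverse event and serious adverse event reporting, and define the symptom outcomes separately.

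- **Sections 6.0 (new calendar row) and 7.0:** *As outcome data for Section 8.0, and separately from adverse event reporting, the presence or absence and CTCAE v4.0 grade of fatigue, nausea and pain are recorded on a case report form at registration and at the follow-up visits in the toxicity window, regardless of attribution.*
- **Section 8.0:** *The toxicity window is [scheduled follow-up visits named by the sponsor in advance]. A symptom counts as present if it is new or of higher grade than at registration. A symptom not assessed is missing, not absent.*

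The grade is needed only so that worsening from registration can be seen. If the forms already hold such a field, name it in Section 8.0 as the source. If the sponsor does not want to collect these items, drop the symptom tests and keep the liver function analysis. In either case, state the sponsor's cut-off for elevated.

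Separately, reconcile the scope and follow-up window in Section 6.0 note H, Section 7.0 and Section 7.2.1, including for patients without a visit 2.

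**Cost:** protocol wording and three form items at existing visits, with no new visits or tests. For example, registration plus three follow-up visits is 4 × 43 = 172 visit entries. The upper limit, reading the quarterly visits as ending at month 12, is registration plus 11 follow-up visits (week 1; months 1, 3, 6, 9, 12, 18, 24, 36, 48, 60), or 12 × 43 = 516, fewer after deaths. The downside is some extra data entry and queries.

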### 7.1 Standard Definitions of Adverse Events (AE) and Serious Adverse Events (SAE)

7.1.1 Adverse Events (AE) is any unfavorable and unintended sign (including an abnormal laboratory finding), symptom or disease temporally associated with the use of a medicinal (investigational) product, treatment or procedure regardless of whether it is considered related to the medical treatment or procedure (*NCI CTEP Guidelines March 28, 2011*)

7.1.2 Serious Adverse Event (SAE) is an AE that is fatal or life threatening, requires inpatient hospitalization or prolongation of existing hospitalization (for > 24 hours), persistent or significant incapacity or substantial disruption of the ability to conduct normal life functions, or is a congenital anomaly/ birth defect, or results in any important medical event that may not result in death, be life threatening, or require hospitalization may be considered an SAE when, based upon appropriate medical judgment, may jeopardize the subject and may require medical or surgical intervention to prevent any of the above outcomes. A "life-threatening" adverse event places the patient at immediate risk of death in the judgment of the investigator or sponsor.

#### 7.1.3 Severity Rating

The investigator will evaluate the severity of each adverse event. NCI Common Terminology Criteria for Adverse Events (CTCAE v.4.0) or study specific toxicity tables provided in the protocol define severity. If not included in CTCAE v.4.0, severity is expressed in numerical grade using the following definitions:

1. Grade 1: Mild-asymptomatic or mild symptoms; clinical or diagnostic observations only; intervention not indicated.
2. Grade 2: Moderate-minimal, local or noninvasive intervention indicated; limiting age appropriate instrumental ADL.
3. Grade 3: Severe-severe or medically significant but not immediately life-threatening; hospitalization or prolongation of hospitalization indicated; disabling; limiting self-care ADL.
4. Grade 4: Life-threatening consequences; urgent intervention indicated.
5. Grade 5: Death related to AE

#### 7.1.4 Attribution/Relationship to study drug

1. Definite – clearly related
2. Probable – likely related
3. Possible – may be related

4. Unlikely – doubtfully related
5. Unrelated – clearly not related

#### 7.1.5 Expectedness

An Expected Adverse Event is one where the specificity or severity is consistent with the current information available from the resources.

An Unexpected Adverse Event is one where the nature, severity, or frequency of the event is related to participation in the research is not consistent with either:

1. The known or foreseeable risk of adverse events associated with the procedures involved in the research that are described in (a) the protocol-related documents, such as the IRB-approved research protocol, any applicable investigator brochure, and the current IRB-approved informed consent document, and (b) other relevant sources of information, such as product labeling and package inserts: or
2. The expected natural progression of any underlying disease, disorder, or condition of the subject (s) experiencing the adverse event and the subjects(s) predisposing risk factor profile for the adverse event.  
*(OHRP Guidance on reviewing unanticipated problems 2007)*

## **7.2 Recording and Reporting Responsibilities of the participating investigative sites and the sponsor**

### 7.2.1 Participating investigative site recording responsibilities:

These are the directions to be utilized by the site's investigator (sub-investigator) and/or study team at the participating site.

1. Upon identification of an AE or SAE, that is possibly, probably or definitely related to the investigational PET CT scans performed, the site investigator will utilize the above definitions to properly classify the event. Each category listed above must be recorded for each event.
2. Any AE or SAE that is possibly, probably or definitely related to the investigational PET CT scans performed, will be recorded in the "AE case report forms" (CRF) and in progress reports with details about the grade and attribution of each episode, action taken with respect to the study drug, and the patient's outcome will be recorded in the CRF. All events that are possibly, probably or definitely related to the investigational PET CT scans performed, will be recorded on case report forms for the duration of the study until they resolve.
3. All SAEs that are possibly, probably or definitely related to the investigational PET CT scans performed, will be recorded on the FDA

MedWatch form 3500a or other sponsor-provided SAE report form. After submitting the initial report it may be necessary to submit follow up reports to the Study Monitor, Sponsor and /or the FDA should the event require further investigation.

7.2.2 Investigative site reporting responsibilities:

1. The investigator/ site is responsible to report all SAEs that are possibly, probably or definitely related to the investigational PET CT scans performed, to the Study Monitor within 24 hours of becoming aware of the event.
2. Each investigator is responsible to report all AEs/SAEs that are possibly, probably or definitely related to the investigational PET CT scans performed; to their local IRB following guidelines set by that IRB. Fox Chase Cancer Center Quality Assurance (QA) reserves the right to request an event be reported to the IRB at their discretion. Copies of events reviewed by the IRB must be sent via fax to the Regulatory Coordinator at [contact].
3. Any investigator who is in doubt of whether a particular AE needs to be reported is directed to call the Study Monitor for confirmation from the PI.

#### 7.2.2.1 Pregnancy

All WOCBP should be instructed to contact the Investigator immediately if they suspect they might be pregnant (e.g., missed or late menstrual period) at any time during study participation.

In the event of a confirmed pregnancy in a patient participating in the study, the Investigator must immediately notify the Fox Chase Cancer Center Study Monitor who will notify the Study PI ([name]).

#### 7.2.3 ERP Reporting Responsibilities:

These are the reporting instructions for the study sponsor.

1. Adverse events which meet all of the following criteria must be reported to all participating institutions for IRB submission within 2 weeks of notification of the event.
  - i. Unexpected (in terms of nature, severity, or frequency) given (a) the research procedures that are described in the protocol-related documents, such as the IRB-approved research protocol and informed consent document; and (b) the characteristics of the subject population being studied;
  - ii. Possibly related to participation in the research (possibly related means there is a reasonable possibility that the incident, experience, or outcome may have been caused by the procedures involved in the research); and
  - iii. Serious (refer to above definition) or otherwise one that suggests that the research places subjects or others at a greater risk of physical or psychological harm than was previously known or recognized.
2. If the adverse event requires modification of the study protocol and informed consent, these changes will be provided to all participating institutions in the form of an amendment from the CTO for each site's IRB of record along with the report of the adverse event.
3. Copies of all related correspondence and reporting documents will be maintained in a centralized regulatory file for this study at CTO.

4. SAEs that are related, unexpected, fatal, or life-threatening are reportable through the Food and Drug Administration (FDA) MedWatch program by telephone or fax no later than 7 calendar days after initial receipt of the information. Further information on the timing of submissions are as directed by FDA guidelines (<http://www.fda.gov/medwatch/index.html>). Serious, unexpected events that suggest significant clinical risk will be submitted to within 15 calendar days after initial receipt of this information.

Food and Drug Administration:  
Telephone [name]  
Fax [name]  
<http://www.fda.gov/medwatch/report.htm>

Mandatory Drug Reporting:  
Central Document Room  
Center for Drug Evaluation and Research  
Food and Drug Administration  
[name]  
[name]

Office of Post-Marketing Drug Risk Assessment (HFD 730)  
Center for Drug Evaluation and Research  
Food and Drug Administration  
[name]  
[name]

[contact] for any further questions regarding where to send drug mandatory reporting forms

